12.3 Proposed primary and secondary questionnaire outcome measures

- We plan to use the following instrument as the potential primary outcome for the future RCT, Me and My Feelings (Deighton et al., 2013). This comprises 16 items, each rated 0 (best) to 2 (worst), measuring emotional (M&MF-E) and behavioral (M&MF-B) difficulties (M&MF-E, ten items; borderline/clinical cut-off >9; M&MF-B, six items; borderline/clinical cut-off >5). The measure is designed specifically for use in schools to evaluate public health initiatives, and has been widely used with children of this age group.

Proposed secondary outcomes for the future RCT are:

- The Children's Outcome Rating Scale (CORS, Duncan, Miller & Sparks, 2003) measures wellbeing/distress across four items, each rated 0 (worst) to 10 (best); clinical cut-off <32. The measure is widely used with children of this age.
- Children complete a quiz assessing learning from CUES-Ed (see Appendix 1). The quiz has been completed by large numbers of children during in-service delivery of CUES-Ed, so is acceptable for completion, with face validity. We are in the process of establishing norms, and will validate the measure as part of this pilot study.
- Teachers complete a rating of whole class behaviour involving estimates of the proportion of the class displaying particular behaviours 'always' or 'never', with the remainder displaying the behaviour 'sometimes'. We will validate this measure as part of this pilot study (see Appendix 2).

In addition:

- *Teacher adherence* data will be collected from a checklist to be standardised during the study.

- *Child attendance* data will be collected from the class register

13. Participant timeline

The delivery timeline needs to fit school terms, so has been designed to accommodate breaks.

Week	Study phase	Activity
-6+	Pre-engagement	
 • Approach local authority
-4+	Engagement	
 • Approach headteachers. • As part of consent, heads check teacher availability. • Headteacher consent • Teacher consent
-3 to -2	Participation, pre-randomisation	
 • Letter, information sheet and consent sent to parents • Classes informed of study by teacher using video from research team
-1 to 0	Baseline	
 • Child assent • Child measures • Teacher measures
0	Randomisation	
 • Research team informs school of allocation
<2	Intervention start (intervention arm only)	
 • Intervention arm teachers watch training video and commence CUES-Ed delivery
8	8-weeks assessment	
 • Child measures • Teacher measures
16	16-weeks assessment	
 • Child measures • Teacher measures • Final point for return of parent consent • Final sort of data into that with consent/assent for research use and that to be securely destroyed
16+	Waitlist control arm offered CUES-Ed at convenient point for school	

The table above summarises the study timeline from first contact.

Following randomisation:

For schools in the intervention arm (CUES-Ed), teachers will watch the instructional video, and start the training. CUES-Ed delivery should start within two weeks of randomisation, and proceed at an hour each week. There are 12 hours of teaching to deliver within the 16-week window. Measures will be completed at 8-weeks post-randomisation and 16-weeks post-randomisation.

For schools in the waitlist control arm (WL), the outcome measures at 8-weeks and 16-weeks will be completed without the class receiving the CUES-Ed programme.

PROTOCOL IDENTIFICATION Amendment number: Original V1 Issue date: 251021 Authors: [name]
Amendment I 010322: Figures for feasibility amended to proportions; proportion of children giving
baseline data added (as logical follow-on from parental consent/child assent rates).

The end of the trial will be defined as the last follow-up assessment at 16 weeks.
Waitlist control participants will then receive CUES-Ed, at a time suitable in the context
of the usual curriculum. This will not be part of the outcomes of the study.

13.3 Table of contacts

[figure not shown]
	Engagement with school	Baseline assessment 0-weeks	Pre-intervention	0-16 weeks	8-weeks	16-weeks
Headteacher consent	X (Research lead/ Headteacher 30 minutes*)					
Parent letter, consent	X (School/parent 30 minutes*)					
Teacher liaison and consent	X (Research team/ Headteacher/ Teacher 30 minutes*)					
Assessment		X (Children 15 minutes)			X (Children 15 minutes)	X (Children 15 minutes)
Randomisation			X (Researcher 24 hours)			
Intervention				X (Teacher/ children 12 x 1 hour**)		
Adherence				X (Researcher/ teacher 1 hour)		

**30 minutes includes 15 minutes to read the information and 15 to discuss/decide*

***Teaching takes places during three 20 minute sessions/week for 12 weeks; with school holidays, the delivery window is expected to be up to 16 weeks*

13.4 Study flow diagram

Figure 1: Design

14. Sample size

We estimate from two classes within 10 schools there will be approximately 600 children and we anticipate that 60% of parents of the children will consent (n=360). We anticipate the key challenge to the success of running the future confirmatory RCT will be to understand the follow up rate. By consenting and collecting baseline data from 360 children we will be able to estimate the follow up rate (assumed to be 80%) with $\pm 4.1\%$.

15: Recruitment

15.1 Schools:

For the feasibility pilot study, we will recruit schools known to the CUES-Ed service, by liaising directly with local authorities and headteachers. Each school will be approached for headteacher consent. Teachers will be approached by their head to discuss participation. However, as the headteacher is also their manager, they will each have a separate meeting with the research team to ensure they have the opportunity to decline participation should they wish to. Heads will agree, as part of their consent on behalf of the school, to teachers being free to decide to participate or otherwise without this compromising their relationship with their school in any way.

15.2 Parents:

Once headteacher and teacher consent is secured, letters will be sent to all parents in the target year group explaining the study and seeking consent to use outcome measures for a research purpose. Parents will receive one telephone follow-up from the school office – they will be asked if they would be willing for the research team to contact them. Parents agreeing to this contact will also be followed up by the

research team. We will also place research team members in playgrounds during drop-off and pick-up times with additional forms for parents to sign.

15.3 Children:

All children will be invited to attend CUES-Ed sessions and complete outcomes, unless parents, or the children themselves request not to participate. This is because it is important that the parental consent process does not result in children feeling excluded or stigmatised. Children will give assent for the use of the measures for research. This will be given as privately as possible, again to avoid any stigma. We will only use data when both parents and children consent.

METHODS: ASSIGNMENT OF INTERVENTIONS

16. Randomisation

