Appendix 1: Study Synopsis

Title of clinical trial	A feasibility, cluster randomised, 16-week, parallel-group pilot study to investigate the feasibility of trial procedures for a larger multicentre comparison of a digital school-based cognitive behavioural resilience/wellbeing-building intervention ('CUES-Ed') targeting emotional and behavioural problems in vulnerable primary school children in whole classes, compared to the usual school curriculum.
Protocol Short Title/Acronym	Building Resilience in Children. The CUES-Ed research project: feasibility study.
Study Phase if not mentioned in title	Feasibility study
Sponsor name	SLaM/KCL
Chief Investigator	[name]
REC number	LRS/DP-21/22-25994
Medical condition or disease under investigation	Emotional and behavioural problems in vulnerable children (scoring at or below borderline/clinical cut-off) receiving the intervention in whole classes
Purpose of clinical trial	To investigate the feasibility of trial procedures
Primary objective	Evaluate trial procedures
Secondary objective (s)	Estimate parameters to determine sample size for a full trial Validate classroom-based outcome measure Standardise teacher adherence rating Validate child quiz
Trial Design	Parallel group cluster RCT
Endpoints	Primary endpoint: post intervention at 16 weeks
Sample Size	We plan to consent 360 children from 10 schools (each with 2 classes)
Summary of eligibility criteria	Inclusion criteria: In Year 4 of a participating school Parental consent/child assent Exclusion criteria: None
Intervention	A cognitive behavioural resilience/wellbeing building intervention, comprising seven modules with 25 learning objectives, delivered weekly to whole classes, on a digital platform, facilitated by teachers

PROTOCOL IDENTIFICATION Amendment number: Original V1 Issue date: 251021 Authors: [name]
Amendment I 010322: Figures for feasibility amended to proportions; proportion of children giving
baseline data added (as logical follow-on from parental consent/child assent rates).

	(Digital CUES-Ed CBT programme, teacher led). The intervention lasts 12 weeks. The delivery window will be 16 weeks to fit school terms. Assessments will be completed at 0, 8 and 16 weeks, within a 1-month window.
Maximum duration of treatment of a Subject	16-weeks
Version and date of protocol amendments	V1 251021

CONTENTS

ITEMS 1-5: ADMINISTRATIVE INFORMATION.....1-2

- 1. Title**
- 2. Trial registration**
- 3. Protocol version**
- 4. Funding**

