8.1 Design

The design will be a parallel group feasibility cluster RCT with random allocation of schools to one of two arms, in a 1:1 ratio.

The usual school curriculum will be delivered without interference in both conditions, with assessments at baseline (0-weeks), 8-weeks and 16-weeks (post intervention, primary endpoint) and a proposed primary outcome of emotional and behavioural problems for vulnerable children at 16-weeks. Waitlist control participants will be offered the intervention later in the term or the following school year. The intervention will be delivered to whole classes; each school will be two or three form entry, and thus comprise two or three classes. Each class will comprise around thirty children

PROTOCOL IDENTIFICATION Amendment number: Original V1 Issue date: 251021 Authors: [name] Amendment I 010322: Figures for feasibility amended to proportions; proportion of children giving baseline data added (as logical follow-on from parental consent/child assent rates).

Schools will be randomised to classes receiving CUES-Ed, in addition to the usual school curriculum, either now (CUES-Ed) or later (waitlist control, WL). The usual school curriculum is nationally set, with limited scope for variation by school. We will record what is delivered in the usual curriculum, but will not interfere with usual delivery. In particular, as CUES-Ed will not comprise additional hours of teaching, we will record any difference arising in the routine curriculum delivered in intervention and control schools.

Trained research workers will complete assessments with children and teachers at baseline (T0), 8-weeks (T1) and 16-weeks (T2, post therapy), see Figure 1.

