18.1 Data collection methods

Outcome measures (child emotional/behavioural problems, child wellbeing, teacher rated class behaviour) will be completed by children and teachers at 0, 8 and 16-weeks, on paper, with support from the research worker as required. Measures will be completed as a group in the classroom. Assessments should occur within a 1-month window of their calendar date, counted from the day of randomisation. Assessments will be collected by teachers, checking child assent and cross-referencing with parental consent. Assessment packs for children with both parental consent and child assent will be stored in the classroom, securely, separately from those without consent/assent. Once the final assessments are completed, the research team will collect the secured data and confidentially destroy, without access, data for children without consent/assent for research use. Data for children with both parental consent and child assent will be returned to the research team's trust base for entry.

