20.1 Primary outcome analysis

The primary feasibility outcomes will be assessed by proportions, with their associated 95% confidence interval. No hypothesis tests will be carried out on these.

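### The ±4.1% precision given for the follow-up rate in section 14 assumes 360 independent children, but the children are clustered in 10 schools, so the figure is too favourable

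*Protocol*

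**What the plan says.** Section 14 builds the sample size from the school structure: "We estimate from two classes within 10 schools there will be approximately 600 children", of whom 60% (360) are expected to have parental consent. It names the follow-up rate as the main thing to learn before the full trial. It then states the precision: "By consenting and collecting baseline data from 360 children", "we will be able to estimate the follow up rate (assumed to be 80%) with" ±4.1%. It mentions no ICC, design effect or other allowance for clustering.

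The rest of the protocol describes a clustered study. Section 8.1 calls it a "parallel group feasibility cluster RCT with random allocation of schools to one of two arms". Section 18.1 says of the assessments: "Measures will be completed as a group in the classroom".

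On analysis, section 20.1 says: "The primary feasibility outcomes will be assessed by proportions, with their associated 95% confidence interval". It names no interval method. Section 20.2 includes random effects for school and class, and reports an ICC, for the Me and My Feelings (M&MF) score only. Section 20 places a statistical analysis plan before database lock.

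**The concern.** A precision statement for a proportion in a cluster design should reflect how much that proportion varies between clusters. Here follow-up depends on things organised by school or class: group assessment sessions, collection of packs by teachers (18.1), and catching absentees within a one-month window (18.2). A whole school may also withdraw up to the start of delivery (22.4), which by the section 13 timeline comes after baseline and randomisation. Children in one school are therefore likely to share the same fate to some degree.

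The ±4.1% is the only quantitative justification of the sample size in the protocol, and it concerns the rate that section 14 puts first. If it is too small, readers will think the pilot pins down follow-up more closely than 10 schools can.

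**Working it through.** **Inputs from the protocol**
- n = 360 children with consent and baseline data; p = 0.80 (section 14).
- 10 schools, two classes each (synopsis, section 14): 360/10 = 36 children per school, 360/20 = 18 per class.
- 95% confidence level. Section 14 gives none; 95% is taken from section 20.1 and reproduces the stated figure.

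**Assumptions, not in the protocol**
- School-level ICC of follow-up between 0.01 and 0.10.
- Equal cluster sizes.

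**Step 1: reproduce the stated figure**

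1.96 × sqrt(0.8 × 0.2 / 360) = 0.0413, or 4.13 points. This matches ±4.1% with a design effect of exactly 1. Other independence-based intervals at 288/360 give much the same: Wilson 4.12, Agresti-Coull 4.13, Clopper-Pearson 4.26 points.

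**Step 2: allow for clustering by school**

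Design effect DE = 1 + (36 − 1) × ICC. Half-width = c × sqrt(0.16 × DE / 360), with c = 1.96 (z) or 2.262 (t, 10 − 1 = 9 df).

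| ICC | DE | Effective n (360/DE) | Half-width, z | Half-width, t (9 df) |
|---|---|---|---|---|
| 0.01 | 1.35 | 267 | 4.8 | 5.5 |
| 0.02 | 1.70 | 212 | 5.4 | 6.2 |
| 0.05 | 2.75 | 131 | 6.9 | 7.9 |
| 0.10 | 4.50 | 80 | 8.8 | 10.1 |

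At ICC 0.05 the z interval around 80% runs from about 73.1% to 86.9%, against 75.9% to 84.1% under independence. The lower limit reaches 70% at an ICC of about 0.14 with z, or about 0.10 with t.

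**Step 3: sensitivity to the level of clustering**

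If all clustering were by class (18 per class, 20 classes), DE = 1 + 17 × ICC. The z half-widths at ICC 0.01, 0.02, 0.05 and 0.10 would be 4.5, 4.8, 5.6 and 6.8 points. These are smaller than with school clustering, but all exceed 4.1.

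**Step 4: a check that needs no ICC**

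Losing one class at follow-up costs 18/360 = 5 points, already more than the claimed half-width. Losing one school costs 36/360 = 10 points.

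**The case against.** Several points on the other side are sound.

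- **Size.** The protocol gives no ICC, so only the direction is certain. At ICC 0.01 with z, ±4.8 is close to ±4.1. Absent children are seen on their return within the window (18.2), which may limit losses tied to a single session. This stands, and it is why a range is shown.
- **Section 20.1.** A reader might infer that the planned confidence intervals for consent, assent, baseline data and follow-up are all too narrow. The protocol does not establish this. Section 20.1 names no method, the analysis plan is still to come, and no precision is stated for consent, assent or baseline data. That clustering is mentioned only for the M&MF suggests simple intervals but does not prove them.
- **Progression decisions.** A reader might also infer that the go/no-go rule is undermined. The criteria in section 12.1 are set on observed proportions and 20.1 excludes hypothesis tests, so a wider interval moves no result between green, amber and red. By normal approximation, if true follow-up were 70%, the chance of observing at least 80% would be about 0.6% at ICC 0.05 (SE sqrt(0.21 × 2.75/360) = 4.0 points, z = 2.50) and 2.5% at ICC 0.10 (SE sqrt(0.21 × 4.5/360) = 5.1 points, z = 1.95). Such probabilities follow from having 10 schools and this threshold; rewording the precision would not alter them.
- **Remedy.** Section 8.1 allows two or three classes per school. A t interval on 10 unweighted school proportions would then estimate the average school's rate, not the pooled child proportion that section 7.1.4 uses (288 of 360). The method must target the pooled proportion.

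None of this rescues the ±4.1% itself. It is a positive statement in the protocol, not a detail left for later.

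**Conclusion.** The concern holds for the precision stated in section 14. ±4.1% is correct arithmetic on an assumption of independence that the 10-school design does not support, and it is too favourable for any positive ICC.

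For an assumed school-level ICC of 0.01 to 0.10, the half-width is 4.8 to 8.8 points (z), or 5.5 to 10.1 points (t, 9 df). That is about 1.2 to 2.1 times the stated value, and up to about 2.4 times with t. These sizes rest on the assumed ICC range and equal clusters of 36.

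For section 20.1 the point is conditional: it applies only if simple binomial intervals are intended. Nor does the finding show that the pilot is too small. Keeping ±4.1 points at ICC 0.05 would take about 1,005 children, or 28 schools of 36 (1.96² × 0.16 × 2.75 / 0.041²), but the protocol sets no precision requirement that would call for this.

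**What to change.** **Section 14.** Replace ±4.1% with a clustering-adjusted range and state the ICC assumption and cluster count behind it. For example: about ±5.5 to ±10 points for a school-level ICC of 0.01 to 0.10 with 10 schools (t, 9 df).

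**Section 20.1.** State that 95% confidence intervals for child-level feasibility proportions allow for clustering by school, using a small-sample method that targets the pooled child proportion. One option is a cluster-robust ratio estimator with t on school-based degrees of freedom. Report the ICC of follow-up, which is also useful for planning the full trial. If the analysis plan already specifies a clustered interval, a cross-reference is enough.

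**Cost.** Wording in two sections. No more schools or children, and no change to the progression thresholds. The downside is a less favourable stated precision.

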16.1 Sequence generation

Randomisation will be carried out following consent and when teachers and children have completed baseline assessment and prior to the start of the intervention. For the pilot study, cluster randomisation will be managed by the study statistician. We will randomise using covariate constrained cluster randomisation balancing on school deprivation and school size (Carter and Hood, 2008).

16.2 Concealment mechanism

Randomisation will be managed by the study statistician. Cluster characteristics needed by the statistician in order to perform the randomisation will be sent through by the trial manager once the school is confirmed as taking part in the study. Allocations will then be sent to the trial manager once all baseline data has been collected from the participants.

16.3 Implementation

Schools will be randomised once baseline assessments are completed. The member of the study team collecting baseline (0-week) measures will alert the study statistician who will send the allocation to the study PI or an allocated deputy from within the research team. This person will communicate with the school and ensure that appropriate steps are initiated (teacher training for intervention schools).

17. Blinding, emergency unblinding

We will not be able to blind participants to treatment group. Similarly, the teachers cannot be blind to allocation as they will deliver the intervention. The RAs completing outcome assessments will be exposed to school interiors decorated with CUES-Ed materials and children's chatter about the intervention (or the absence of these indicators) and thus will not be blind to allocation. However, once collected, data will be processed by RAs blind to allocation.

Baseline assessments will be carried out blind to treatment allocation. Follow-up assessments cannot be blinded. Once data is collected, it will be processed by

researchers blind to treatment allocation. Emergency unblinding will not be necessary.

18. Data collection

18.1 Data collection methods

Outcome measures (child emotional/behavioural problems, child wellbeing, teacher rated class behaviour) will be completed by children and teachers at 0, 8 and 16-weeks, on paper, with support from the research worker as required. Measures will be completed as a group in the classroom. Assessments should occur within a 1-month window of their calendar date, counted from the day of randomisation. Assessments will be collected by teachers, checking child assent and cross-referencing with parental consent. Assessment packs for children with both parental consent and child assent will be stored in the classroom, securely, separately from those without consent/assent. Once the final assessments are completed, the research team will collect the secured data and confidentially destroy, without access, data for children without consent/assent for research use. Data for children with both parental consent and child assent will be returned to the research team's trust base for entry.

18.2 Retention

Children will be assessed in the classroom. Absent children and teachers will be followed up on their return to school, providing this falls within the 1-month window.

19. Data management

19.1 Data forms and entry

Data will be collected in paper format and will be entered onto a secure web application REDCap, with integrated participant and range checks. Paper forms will be stored securely by the research team until the end of the study (January 2023).

19.2 Data transmission and editing

Separate databases will be created for school level data, child level data, teacher adherence data, and allocation. The database will be designed to only accept within range responses. Range and value checks and spot checks against paper copies will be employed to check data.

